7.3 Rules for Missing Data

Missing data will not be imputed, except for missing date information for AEs and concomitant medications. The imputed dates will be used to determine the treatment-emergent period. For AEs with a partial date, available date parts (year, month, and day) of the partial date will be compared with the corresponding date components of the start date and end date of the treatment-emergent period to determine if the event is treatment emergent. When in doubt, the AE will be considered treatment emergent by default. The following rules will be applied to impute partial dates for AEs:

- If start date of an AE is completely or partially missing, impute as follows:
 - If both month and day are missing and year = year of first dose date, then set to first dose date.
 - If both month and day are missing and year \neq year of first dose date, then set to January 1.
 - If day is missing and month and year = month and year of first dose date, then set to first dose date.
 - If day is missing and month and year \neq month and year of first dose date, then set to first of the month.
 - If start date is completely missing and AE end date is on or after the first dose date, set to first dose date.
 - If start date is completely missing and AE end date is prior to the first dose date, do not impute an AE start date.
- If end date of an AE is partially missing, impute as follows:
 - If both month and day are missing, then set to December 31.
 - If only day is missing, then set to last day of the month.
 - If end date is completely missing, do not impute.

When the start date or end date of a medication is partially missing, the date will be imputed to determine whether the medication is prior or concomitant (or both). The following rules will be applied to impute partial dates for medications:

- If start date of a medication is partially missing, impute as follows:
 - If both month and day are missing, then set to January 1.
 - If only day is missing, then set to the first of the month.
- If end date of a medication is partially missing, impute as follows:
 - If both month and day are missing, then set to December 31.
 - If only day is missing, then set to last day of the month.
- If start date or end date of a medication is completely missing, do not impute.

Listings will show the original date information without imputation, but derived parameters (TEAE indicator and duration of AE) will be flagged to indicate the type of imputation performed.

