30 minute post-injection observation j	May be completed while the subject is receiving dialysis.
Instruction to subjects on collection of oral temperature and PIRs k	Subjects will be provided with a diary to record oral temperature and post-injection reactions.
Assessment of MAEs, SAEs, AMIs, and AESIs l	SAEs will be collected and followed through EOS Visit. If the SAE is assessed as possibly or probably related to study treatment, it must be followed until it is considered stable or resolved, including beyond EOS Visit. MAEs, AMIs, and AESIs will be collected and followed through EOS Visit. Further details regarding safety monitoring of AMIs and AESIs are provided in Section 9.4.7.2.
Concomitant medications m	Concomitant medications are all medications and non-study vaccines received by the subject from the first injection through Week 28 or Early Discontinuation. Use of vitamins and dietary supplements will not be collected unless they are indicated as a concomitant therapy for conditions directly related to undergoing hemodialysis. After Week 28, only prescription medication or over-the-counter drug taken by the subject for the treatment of MAEs, SAEs, AMIs, or AESIs will be recorded on the eCRF through EOS Visit (further details regarding safety monitoring of AMIs and AESIs are provided in Section 9.4.7.2).

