7.0 DEFINITIONS, COMPUTATIONS, AND CONVENTIONS

7.1 Definitions and Computations

Study Day

Study day will be calculated in reference to the date of first injection (Day 1). For visits conducted on or after the first injection date, study day is calculated as (visit date – first injection date + 1). For visits conducted before the first injection date, study day is calculated as (visit date – first injection date). There will be no Day 0.

Date of First Injection and Date of Last Injection of Study Vaccine

The date of the first injection of study vaccine is defined as the date a patient receives the first injection of the study vaccine. The date of the last injection of study vaccine is the date a patient receives the last injection of the study vaccine.

Treatment-Emergent Period

In this trial, only medically attended adverse events (MAEs), AEs for which a subject seeks medical attention at a doctor's office, clinic, study site, emergency room, or is hospitalized, will be collected.

The reporting period for all non-serious MAEs begins at the time of the first study injection (Day 1) through EOS Visit. All MAEs will be captured on the MAE eCRF.

Any SAE that occurs from the time the consent is signed through EOS Visit, whether or not the SAE is related to the study treatment, must be reported.

The treatment-emergent period is defined as time from the first study injection through EOS visit.

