7.2 Conventions

Unless otherwise specified, the following conventions will be applied to all analyses:

- 1 year = 365.25 days. Year is calculated as (days/365.25) rounded up to 1 significant digit.
- 1 month = 30.4375 days. Month is calculated as (days/30.4375) rounded up to 1 significant digit.
- Age will be calculated by the following SAS code:

If only year of birth is given, then Age = (Year of Screening – Year of Birth). Otherwise

```
age = floor ((intck('month', birth_date, consent_date) -  
(day(consent_date) < day(birth_date))) / 12);
```

- 1 pound = 0.454 kg
- 1 inch = 2.54 cm
- Missing safety data will not be imputed unless otherwise specified.
- For immunogenicity results, anti-HBs concentrations, are obtained using the Elecsys Anti-HBs II assay. For concentration reported as <value, half of the value will be used in calculation. For concentration reported as >value, value+1 will be used in calculation.
- For safety analyses, percentages will be calculated based on the number of patients in the analysis population.

- For by-visit observed data analyses, percentages will be calculated based on the number of patients with nonmissing data as the denominator unless otherwise specified.
- For other continuous endpoints, the summary statistics will include mean, standard deviation, median, and range (minimum and maximum).
- For categorical endpoints, the summary statistics will include counts and percentages.
- MAEs and medical history will be coded using the Medical Dictionary for Regulatory Activities (MedDRA) version 17 or higher.
- Prior therapies and concomitant medications will be coded using the World Health Organization (WHO) Drug Dictionary.

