9.4 Prior and Concomitant Medications

Prior and concomitant medications will be coded using the World Health Organization (WHO) Drug Dictionary (Version 201506 or higher). Prior medications are drugs and therapies used before the first dose date. Medications or therapies are considered concomitant if exposure occurs after the first dose date. The number and percentage of patients with concomitant medications will be presented alphabetically by anatomical therapeutic chemical (ATC) class and by decreasing order of frequency of preferred terms within each ATC class for the safety population. Patients taking the same medication multiple times will be counted once per medication.

All medications recorded on the case report form will be listed.

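### SAP date rules misclassify at Day 1: an SAE known to have ended before the first injection can count as treatment-emergent, and a drug used only on Day 1 is neither prior nor concomitant

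*SAP*

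**What the plan says.** **Adverse-event dates.** SAP 7.3 imputes incomplete start dates and states: "The imputed dates will be used to determine the treatment-emergent period". When only the day is missing the rule is "If day is missing and month and year = month and year of first dose date, then set to first dose date". When day and month are both missing it is "If both month and day are missing and year = year of first dose date, then set to first dose date". Neither has a condition on the end date. For a completely missing start date the list does look at the end date: "If start date is completely missing and AE end date is prior to the first dose date, do not impute an AE start date". The same section resolves doubtful cases as treatment-emergent.

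SAP 7.1 runs the treatment-emergent period from the first injection to the End-of-Study visit. It also requires reporting of "Any SAE that occurs from the time the consent is signed through EOS Visit", so SAEs from the screening period are in the database. Protocol 10.3.2 puts all SAEs on the MAE form, where the date rules apply. Non-serious events are collected only from the first injection, so the matter concerns SAEs alone.

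**Medications.** SAP 9.4 defines prior medications as those used before the first dose date, and then: "Medications or therapies are considered concomitant if exposure occurs after the first dose date". Protocol Appendix 1 draws the line at the injection. Medication history is what was received before it, and "Concomitant medications are all medications and non-study vaccines received by the subject from the first injection through Week 28 or Early Discontinuation".

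**The concern.** The authors of SAP 7.3 saw that an event which ended before dosing must not be moved into the treatment-emergent period, but they guarded only one branch of the rule. An SAE with no start date at all is handled correctly. The same SAE with a known start month is not, so more information gives a worse answer. The result feeds a primary endpoint (SAP 4.0: proportion of subjects with treatment-emergent SAEs, AMIs or deaths) and the derived event duration. The Week 20 report (SAP 8.0) will include MAE data that are not yet fully validated, and incomplete dates are most likely to remain at that stage.

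The medication definitions fail even with complete dates. SAP 7.3 expects every medication to be prior, concomitant or both, but the first dose date itself belongs to neither class. A programmer must either follow the text and leave some drugs unclassified, or depart from it without authority.

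**Working it through.** The plan states no figure to reproduce here. The check applies the rules literally.

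**Inputs.** Start-date rules: SAP 7.3. Treatment-emergent period and SAE collection window: SAP 7.1. Screening of up to 28 days: Protocol 4.1 and Appendix 1. Planned enrolment of about 115: SAP 5.0. Enrolment means receipt of the first injection (Protocol 5.1), so about 115 is also the safety denominator.

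**Step 1: worked example.** The dates are illustrative: first injection 20 March 2020, SAE ended 10 March 2020.

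| Recorded start | Imputed start | Class | Duration (end − start + 1) |
|---|---|---|---|
| March 2020, day missing | 20 March | treatment-emergent | 10 − 20 + 1 = −9 days |
| 2020, day and month missing | 20 March | treatment-emergent | −9 days |
| completely missing | none | not treatment-emergent | none |

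**Step 2: how widely the rule misfires.** Take every onset from Day −28 to Day −1 and every end from onset to Day −1. That is 28 × 29 / 2 = 406 pairs. Repeat for each first-dose date from 1 July 2019 to 30 June 2020 (366 dates, assumed only for the enumeration): 366 × 406 = 148,596 patterns, all ending before the injection.

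- Day missing: 56,028 / 148,596 = 37.7% are classed as treatment-emergent, every one with its start after its end.
- Day and month missing: 140,882 / 148,596 = 94.8%.
- With an end-date check added to both rules: 0.

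These are shares of possible date patterns, not expected event rates.

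**Step 3: effect on the endpoint.** One wrongly counted subject adds 1/115 = 0.87 percentage points, but only if that subject has no genuine treatment-emergent SAE, AMI or death. Day 477 is 476 days after Day 1, or 476/365.25 = 1.30 years. Assume 0.5 to 2 SAEs per person-year and a Poisson process; the documents give no rate. A genuine treatment-emergent SAE would then occur in 1 − exp(−0.65) = 48% to 1 − exp(−2.61) = 93% of subjects. For them the error leaves the proportion unchanged.

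**Step 4: medications, first dose 20 March.**

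| Use | Prior (SAP) | Concomitant (SAP) |
|---|---|---|
| 19 March only | yes | no |
| 20 March only | no | no |
| 19–20 March | yes | no |
| 20–21 March | no | yes |

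Under the protocol, the second row is concomitant if the drug was given after the injection and history if before.

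**The case against.** The best defence of 7.3 is its default that doubtful events count as treatment-emergent. That is a deliberate conservative choice, and it stands wherever the SAE was ongoing at injection or its end date is missing or inconclusive. It does not cover an end date known to precede the injection, because nothing is then in doubt. The accompanying comparison of date parts does not help either, since it uses only the parts of the partial date.

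The objections on size stand. A reader might infer that several primary-endpoint events are at risk. Under the assumed rates, 115 subjects with 14 to 28 days of screening give 115 × 14/365.25 × 0.5 = 2.2 to 115 × 28/365.25 × 2 = 17.6 screening SAEs. The documents do not support reading these as misclassified events. The count has no filter for an end before dosing and no rate of missing days. It also ignores that subjects must be clinically stable and are rechecked before injection. SAEs are reportable within 24 hours of awareness, so a missing day should be uncommon. The error also over-counts rather than hides events, and listings show the original dates.

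A reader might also infer that the Day 1 gap removes the drugs given for acute reactions. It removes only a medication used on Day 1 and never again. Later use brings the drug into the table, dialysis drugs recur, and every recorded medication is still listed. Per-protocol exclusion has its own medication window (SAP 9.2), so no endpoint or analysis population depends on the gap.

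Finally, the instruction in SAP 7.2 that years and months are "rounded up to 1 significant digit" may look like a third fault of the same kind. No planned summary depends on it, and age has its own code, so it is not part of this point.

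**Conclusion.** Both faults are real on the literal text, and both are minor. The adverse-event error needs four things together: a subject who was dosed, a screening SAE, a partial start date whose known parts match the first dose date, and an end date known to precede the injection. How often that happens cannot be estimated from the documents. When it does, the SAE/AMI/death proportion rises by at most about 0.87 points per subject, and by nothing if the subject has another qualifying event. The bound assumes about 115 subjects in the safety population. The medication gap affects only the concomitant summary table. Neither fault supports a claim that the primary safety results would be materially biased. The case for acting is that stated rules give wrong classifications and cost almost nothing to correct.

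**What to change.** In SAP 7.3, add a rule that takes precedence over the partial-start rules: if the AE end date, or the latest date consistent with a partial end date, is before the first dose date, the event is not treatment-emergent and its start date is not imputed to the first dose date. State what happens to the start instead. Leaving it unimputed matches the existing branch for a completely missing start. Using the first of the known month, or 1 January, matches the other branches, and is what the check in Step 2 used. Treatment-emergent status is the same either way; only the derived duration differs (missing, against 10 or 70 days in the worked example). Keep the existing default for all other cases.

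In SAP 9.4, define concomitant as exposure on or after the first dose date. Where the time of injection and of drug use are recorded, class Day 1 use before the injection as prior, in line with Protocol Appendix 1.

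The cost is two SAP wording changes and the matching derivation code. No new data are needed.

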8.0 TIMING OF ANALYSES

A preliminary analysis may be performed to assess the primary immunogenicity objective of the SPR at Week 20 after approximately 50 subjects have completed their Week 20 visit (see Section 9.9).

A final immunogenicity report with data up to Week 20 will be produced including demographics, baseline characteristics, medical history, vaccine exposures, immunogenicity data and post-injection reaction data. These data will be verified as complete and final following database lock process, and major protocol deviations up to Week 20 have been identified. Safety analysis of MAEs and concomitant medications with non-fully validated and non-final data will be included in this report. Status of these data will be footnoted where applicable.

Final analyses will be carried out after the last participant has completed their last study visit, the study database has been authorized by Dynavax as complete and final, and major protocol deviations have been identified. Any changes to the frozen data in the final immunogenicity report with data up to Week 20 will follow post database lock change process according to BRK-SOP [REDACTED] Clinical Study Database Lock-Unlock Authorization.

9.0 STATISTICAL METHODS

This is an open-label, single arm study, evaluating the immunogenicity and safety of HEPLISAV-B® in adults with end-stage renal disease undergoing hemodialysis. No pre-specified hypothesis testing will be performed. All analyses of demographics and baseline

characteristics, medical history, vaccine exposure, immunogenicity and safety will be summarized in a descriptive manner.

All confidence intervals are two-sided 95% confidence intervals unless otherwise specified.

In general, continuous variables will be summarized by sample size, mean, standard deviation, median, quartiles, minimum and maximum, and categorical variables will be summarized by counts and percentages. All data processing, summarization, and analyses will be performed using SAS Version 9.3 or higher. Specifications for tables, graphs, and data listings will be provided in the tables, figures, listings (TFL) specifications document if needed.

9.1 Patient Disposition

Patient disposition will be summarized for all enrolled patients including patients in the safety, PP and mITT populations and patients discontinuing the study along with the reasons for discontinuation (as documented on the case report form Study Completion).

A listing of patients discontinuing the study after enrollment will be produced.

9.2 Protocol Deviations

For the purpose of selecting subjects for the per-protocol population, a major protocol deviation is defined as one of the following:

- not meeting one or more enrollment criteria,
- anti-HBs serum sample obtained outside protocol specified visit window 4 weeks following the fourth study injection (Week 20 ± 7 days)
- 28 days prior to Injection 1 and through Week 20: received prohibited concomitant medications comprising systemic corticosteroids, other immunomodulators or immune suppressive medications (with the exception of inhaled steroids), immunoglobulin, DNA plasmids or oligonucleotides, or any other investigational medication.

A listing of patients with major protocol deviations will be provided describing their deviations. Any exclusions from analysis populations due to protocol deviations and other reasons will also be listed.

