**90 days prior to Injection 1 and through Week 28:**

- Blood products or immunoglobulin

If a subject requires treatment that is prohibited, the investigator should contact the Dynavax medical monitor or designee to determine whether the subject should receive further study injections. If the subject is not eligible for subsequent study injections, **the subject will not be withdrawn from the study, but** will be followed for safety through End-of-Study (EOS) Visit.

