## **11.2 Study Analysis Populations**

The Safety Population will comprise all subjects who received at least 1 study injection, excluding subjects who have no on-study safety data.

The Per-protocol (PP) Population for the immunogenicity analysis will comprise all subjects who receive all study injections, have no major protocol violations (to be specified in the Statistical Analysis Plan), and have anti-HBs levels obtained within the study visit window at Week 20.

The modified intent-to-treat (mITT) population for the immunogenicity analysis will comprise all subjects who receive at least 1 study injection and have at least 1 post-injection immunogenicity evaluation.

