**APPENDIX 1: SCHEDULE OF ASSESSMENTS (CONT'D)**

**Footnotes**

Early Discontinuationa	The assessments at the Early Discontinuation Visit should occur 28 days or more after the last study injection.
Medical and medication history b	Medical and medication history are all medical events occurring and medications received by the subject prior to the first study injection.
Height and weight c	Height and weight are only collected at Screening.
Physical examinations d	A full physical examination (excluding pelvic/genital, rectal, and breast examination) will be conducted at Screening, and a targeted physical examination based on subject-reported symptoms (excluding pelvic/genital, rectal, and breast examination) will be conducted at each study injection visit and End-of-Study (EOS) Visit or Early Discontinuation Visit. If a subject discontinues study treatment, subsequent targeted physical examination is only required at EOS Visit or Early Discontinuation Visit.
Serum pregnancy test (for WOCBP) e	All female subjects, regardless of age, are considered to be women of child bearing potential (WOCBP) except if they have been post-menopausal for at least 1 year or surgically sterile for at least 1 year. Samples will be collected prior to study drug injection. All pregnancy test results must be negative prior to injection.
Urine pregnancy test (for WOCBP) e,f	All female subjects, regardless of age, are considered to be women of child bearing potential (WOCBP) except if they have been post-menopausal for at least 1 year or surgically sterile for at least 1 year. Samples will be collected prior to study drug injection. All pregnancy test results must be negative prior to injection. Dipstick can be used for urine pregnancy test.
Anti-HBs (quantitative) and stored serum and plasma aliquot g	There must be a minimum of 21 days between any study injection and the subsequent anti-HBs sample collection. On treatment days, samples will be collected prior to study injection. Extra aliquots of serum and plasma will be collected and may be stored frozen for future use.
Weeks 28 and 42 h	Week 28 and 42 assessments (assessment of SAEs; MAEs, AESIs, AMIs; and concomitant medication) will be completed via telephone call.
Study injection (HEPLISAV-B®) i	Blood collection and HEPLISAV-B administration must be performed prior to the start of dialysis on study visit days.

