6.3 Efficacy Population

The per-protocol (PP) population for the immunogenicity analysis will comprise all subjects who receive all study injections, have no major protocol deviations (see Section 9.2), and have anti-HBs levels obtained within the study visit window at Week 20. PP population is defined for Week 20 visit, but will be used in analyses at other visits where applicable.

The modified intent-to-treat (mITT) population for the immunogenicity analysis will comprise all eligible subjects who receive at least 1 study injection and have at least 1 post-injection immunogenicity evaluation.

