9.6 Immunogenicity Analyses

Immunogenicity data will be analyzed based on the PP population by visit for all visits through 20 weeks with immunogenicity data collected.

The SPR will be estimated. The associated 2-sided 95% confidence interval will be calculated using the Clopper-Pearson method.

Proportion of subjects with anti-HBs concentration ≥ 100 mIU/mL and associated 2-sided 95% confidence interval will also be calculated using Clopper-Pearson methods.

Anti-HBs geometric mean concentration (GMC) and associated 2-sided 95% confidence interval will be calculated by exponentiating the mean and confidence interval in \log_{10} of the anti-HBs concentration assuming Normal distribution.

Analyses based on the mITT population may also be conducted.

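### The SAP's per-protocol exclusions name immunoglobulin but not blood products, so a subject given blood products between Injection 4 and the Week 20 sample stays in the primary seroprotection rate

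*SAP*

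**What the plan says.** Protocol 11.2 limits the PP population to subjects who, among other conditions, "have no major protocol violations (to be specified in the Statistical Analysis Plan"). The protocol therefore leaves the list to the SAP. SAP 6.3 picks this up: the PP population will "comprise all subjects who receive all study injections, have no major protocol deviations (see Section 9.2"), with a Week 20 anti-HBs result inside the visit window.

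SAP 9.2 gives the list. Its third bullet runs from 28 days before Injection 1 through Week 20 and covers any subject who "received prohibited concomitant medications comprising systemic corticosteroids, other immunomodulators or immune suppressive medications (with the exception of inhaled steroids), immunoglobulin, DNA plasmids or oligonucleotides". The bullet ends with investigational agents of any kind. Immunoglobulin is named and blood products are not.

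The protocol does not separate the two. Exclusion criterion 6c bars "Blood products or immunoglobulin" in the 90 days before the first injection. Protocol 7.2 prohibits the same paired item from 90 days before Injection 1 through Week 28.

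SAP 9.6 makes PP the analysis set for the primary rate: "Immunogenicity data will be analyzed based on the PP population by visit". An analysis in the modified intent-to-treat (mITT) population is optional.

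**The concern.** By naming immunoglobulin, the SAP accepts that this kind of exposure disqualifies a subject from the primary immunogenicity analysis. It leaves out the other half of the protocol's own pair without saying why. The only reason recorded in the SAP revision history for a change to the PP deviations concerns COVID-19 and injection visit windows.

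The endpoint is the share of subjects with anti-HBs of at least 10 mIU/mL at one visit. If blood products carried enough antibody to reach that threshold, a non-responder would be counted as a responder. A single-arm study has no comparator in which the same error would appear and partly cancel. The exposed window is the one immediately before the primary sample.

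**Working it through.** **Step 1. Can any other rule remove the subject?** Take a subject given blood products only after Injection 4 (Week 16) and before the Week 20 sample.

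| Route out of PP | Source | Does it apply? |
|---|---|---|
| Enrollment criterion not met | SAP 9.2, first bullet; Protocol 5.2, 6c | No. 6c covers only the 90 days before Injection 1 |
| Not all injections received | SAP 6.3; Protocol 7.2 and 8.1 | No. Stopping treatment for a prohibited medication cannot act once Injection 4 has been given |
| Week 20 sample out of window | SAP 6.3 and 9.2, second bullet | No. The sample is in window |
| Prohibited medication | SAP 9.2, third bullet | Not as written. Blood products are not named |

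The subject stays in PP. The mITT population would keep the same subject, so it is no check. Exposure before Injection 4 is not part of this point, because the second route may act there.

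**Step 2. Length of the window.** Injection 4 is on Day 113 and the sample on Day 141, each ±7 days (Protocol Appendix 1).

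- Nominal: 141 − 113 = 28 days.
- Longest with both visits in window: 148 − 106 = 42 days.
- Shortest: 21 days, because "There must be a minimum of 21 days between any study injection and the subsequent anti-HBs sample collection".

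**Step 3. The plan's own precision.** The two-sided 95% Clopper-Pearson limits for x of n are the 2.5% quantile of Beta(x, n − x + 1) and the 97.5% quantile of Beta(x + 1, n − x). For 86/100 this gives 77.6% to 92.1%, width 0.145, which matches SAP Table 5-1.

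**Step 4. Effect of false responders.** One subject counted as a responder through passive antibody moves 86/100 to 87/100 = 87.0% (78.8% to 92.9%), a rise of one point. Half the planned width is 14.5 / 2 = 7.25 points, so a shift of that size needs 8 false responders.

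A false responder must otherwise be a non-responder, and at 86% only 14 of 100 are. Suppose exposure is unrelated to response and every exposed subject reaches 10 mIU/mL. Then one false responder implies about 1 / 0.14 ≈ 7 exposed subjects, and eight imply about 8 / 0.14 ≈ 57.

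**Step 5. Effect of removing exposed subjects.** The documents give no count of exposed subjects, so k below is an assumption. The two columns are the extremes, starting from 86/100.

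| k removed | All seropositive | All seronegative |
|---|---|---|
| 1 | 85/99 = 85.9% (77.4 to 92.0) | 86/99 = 86.9% (78.6 to 92.8) |
| 3 | 83/97 = 85.6% (77.0 to 91.9) | 86/97 = 88.7% (80.6 to 94.2) |
| 5 | 81/95 = 85.3% (76.5 to 91.7) | 86/95 = 90.5% (82.8 to 95.6) |

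The change from 86% runs from −0.7 to +4.5 points. The right-hand column shows what the exclusion could do to the estimate. It is not evidence of bias, since a seronegative subject cannot be a false responder.

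**The case against.** The strongest reply is that the SAP was free to choose. Protocol 11.2 hands the list to the SAP, and SAP 9.2 is plainly not a copy of Protocol 7.2. It also omits live and inactivated vaccines and G-CSF/GM-CSF, and it adds DNA plasmids and oligonucleotides, which 7.2 does not list. A prohibited treatment need not be a major deviation. This stands: the documents do not show that the omission is a mistake. It does not explain why the SAP kept one half of a paired item and dropped the other.

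Second, nothing in the documents says that blood products carry anti-HBs at or above 10 mIU/mL, or how often they are given. This also stands. The harm is conditional, and Step 4 shows that many subjects would have to be exposed before the rate moved much. SAP 9.0 adds that "No pre-specified hypothesis testing will be performed", so no test result can be changed.

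Third, adding a post-baseline exclusion can itself raise the SPR, as Step 5 shows. That is a reason to report both results, not to leave the rule unexplained.

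Fourth, data capture is inferred. Protocol 9.4.9 and the concomitant-medication footnote in Appendix 1 do not name blood products. Protocol 7.2 does list them as non-study medications, medications are recorded through Week 28, Protocol 8.3 sends supportive therapies to the eCRF, and SAP 9.4 counts therapies as well as drugs. Capture is likely but should be confirmed.

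**Conclusion.** The concern holds, as a minor one. As written, a subject exposed to blood products only between Injection 4 and the Week 20 sample, nominally 28 days, counts in the primary SPR although the protocol prohibits that exposure in that window. No other PP criterion removes the subject.

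This rests on reading the SAP's prohibited-medication bullet as a closed list. If it was meant to be open, PP membership becomes a matter of interpretation in an open-label study, which the same edit would settle.

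The effect on the SPR cannot be sized from the documents. Each false responder adds one point at N = 100, and the total is probably small against a 14.5-point interval.

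**What to change.** In the third bullet of SAP 9.2, put blood products beside immunoglobulin. Do this before the Week 20 lock, when "major protocol deviations up to Week 20 have been identified". Report the Week 20 SPR with and without the subjects this removes. If blood products were left out on purpose, give the reason in SAP 9.2 and still show the SPR without the exposed subjects. Confirm first that the eCRF captures blood products.

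The cost is one phrase in the SAP and one table row, with no new data collection apparently needed. A few subjects may leave the PP population, with little loss of precision. With three removed from 86/100, the interval width is 0.149 if all were seropositive and 0.136 if all were seronegative, against 0.145 with none removed.
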